3.1 Dosage and Administration Schedule

Copanlisib is given intravenously at a dose of 60 mg over 1 hour on day 1, 8, and 15 in a 3 week on/1 week off schedule. Each cycle is 28 days and cycles are repeated until progression. Please see Section [3.5](#) for dose modifications.

The use of corticosteroids as antiemetics prior to copanlisib administration is not allowed. After administration, flush the line with 0.9 % sodium chloride to ensure complete dose is given. No IV glucose preparations should be administered on the days of infusion.

Rev. Add16

Blood pressure measurement on treatment days

Blood pressure will be measured prior to each copanlisib dose (no more than 4 measurements) until there are two consecutive results <150/90 mmHg with at least a 15 min interval between the measurements to be able to start the infusion of the study medication (pre-dose). The investigator can consider a medical intervention to maintain blood pressure in values appropriate for infusion. The investigator must delay the infusion until blood pressure values are below 150/90.

On copanlisib infusion days, blood pressure will be measured at pre dose, 30 min after the start of infusion, right after the end of infusion; and 1 h and 2 h after the end of copanlisib infusion.

NOTE: Time window of \pm 10 min is allowed for all post dose blood pressure measurements.

Rev. Add16

Recommendations on meal timing on copanlisib infusion days

Because of an inhibitory effect on PI3K α -isoform, which is implicated in insulin metabolism, copanlisib infusions could be associated with temporary increase in blood glucose. Consuming meals in close proximity to copanlisib infusion may exacerbate a glucose level increase.

On infusion days a low carbohydrate diet is recommended, the timing and content of meal intake and additional glucose testing (if clinically indicated) is managed and monitored by the investigators based on glucose response patterns during prior treatment days.

All glucose measurements done at the site, oral glucose lowering medication and/or insulin administration, if applicable, pre-dose fasting/non-fasting status and meal intake timing on infusion days should be documented.

Pre-dose glucose levels

Period	Pre-dose glucose levels
Day 1 of cycle 1	< 160 mg/dL (fasting) < 200 mg/dL (non-fasting)
Day 1 of subsequent cycles	< 160 mg/dL (fasting) < 200 mg/dL (non-fasting)
Days 8 and 15 of each cycle	< 160 mg/dL (fasting) < 200 mg/dL (non-fasting)

The study drug will be administered only if pre-dose glucose level is < 160 mg/dL (fasting) or < 200 mg/dL (non-fasting).

Glucose monitoring is required before and after each copanlisib infusion. The glucose testing is scheduled as follows:

- On Cycle 1 Day 1: Glucose test (finger stick or serum glucose) is performed before starting copanlisib IV infusion at time 0 hour. Additional measurements to be performed at the clinic as clinically indicated at the investigator's discretion.
- On Cycle 1 Days 8 and 15 and all treatment days in subsequent cycles: Glucose test (finger stick or serum glucose) is performed before starting copanlisib IV infusion at time 0 hour. Additional measurements to be performed at the clinic as clinically indicated at the investigator's discretion).
- Review of the blood glucose measurements/meal timing/insulin administration/oral glucose lowering medication, if applicable.

NOTE: If patient needs to take a meal, then glucose test should be taken prior to meal intake.

Monitoring of diabetic patients

- If the patient already monitors his/her blood glucose as part of routine antidiabetic care, the routine measurements should not be replaced by the study specific measurements.

3.2 General Concomitant Medication and Supportive Care Guidelines

Because there is a potential for interaction of copanlisib with other concomitantly administered drugs, the case report form must capture the concurrent use of all other drugs, over-the-counter medications, or alternative therapies. The Principal Investigator should be alerted if the patient is taking any agent known to affect or with the potential for drug interactions. The known potential targets for drug interaction are CYP3A4 inducers or inhibitors, as well as drugs modulating glucuronidation, P-gp, BCRP, and MATE2K function. [Appendix II](#) (Patient Drug Information Handout and Wallet Card) should be provided to patients.

Substrates of P-gp and/or BCRP with narrow therapeutic index should be used with caution and patients monitored for any sign of toxicity. Furthermore, sensitive substrates of the renal drug transporter MATE2K (e.g. metformin) need to be used with caution. Metformin should be interrupted for 48 hours after receiving iodinated contrast media.

Patients taking medications with narrow therapeutic index should be proactively monitored if these medications cannot be avoided. These medications may include quinidine, cyclosporine, and digoxin.

Patients should stop using herbal medications at least 7 days prior to the first dose of copanlisib. Herbal medications include, but are not limited to: St. John's Wort, Kava, ephedra, gingko biloba, dehydroepiandrosterone (DHEA), yohimbe, saw palmetto, black cohosh and ginseng.

Prophylactic antiemetics may be administered according to standard practice. The routine use of standard antiemetics, including 5-HT3 blockers, such as granisetron, ondansetron, or an equivalent agent, is allowed as needed. The use of corticosteroids as antiemetics prior to copanlisib administration will not be allowed.

3.3 Adverse Event Reporting Requirements

The Adverse Event Reporting Requirements for all EAY131 sub-protocols are outlined in the MATCH MASTER protocol. Please refer to those guidelines when determining if an event qualifies as a Serious Adverse Event (SAE) and requires expedited reporting via CTEP's Adverse Event Reporting System (CTEP-AERS).

In addition, the following section outlines agent specific requirements and must be followed to ensure all reporting requirements are met.

3.3.1 Additional instructions, requirements and exceptions for protocol EAY131 – Subprotocol Z1F

Additional Instructions

For instructions on how to specifically report events that result in persistent or significant disability/incapacity, congenital anomaly, or birth defect events via CTEP-AERS, please contact the AEMD Help Desk at [contact] or [contact]. This will need to be discussed on a case-by-case basis.

EAY131 – Subprotocol Z1F specific expedited reporting requirements:

- **Pregnancies:** Pregnancies and suspected pregnancies (including a positive or inconclusive pregnancy test, regardless of age or disease state) occurring while the subject is on copanlisib, or within 28 days of the subject's last dose of copanlisib, are considered immediately reportable events. The pregnancy, suspected pregnancy, or positive/ inconclusive pregnancy test must be reported via CTEP-AERS within 24 hours of the Investigator's knowledge. Please refer to Appendix VIII in MATCH Master Protocol for detailed instructions on how to report the occurrence of a pregnancy as well as the outcome of all pregnancies.

EAY131 – Subprotocol Z1F specific expedited reporting exceptions:

For Subprotocol Z1F, the adverse events listed below **do not** require expedited reporting via CTEP-AERS:

- If an AE meets the reporting requirements of the protocol, and it is listed on the SPEER, it should **ONLY** be reported via CTEP-AERS if the grade being reported exceeds the grade listed in the parentheses next to the event.

3.3.2 Second Primary Cancer Reporting Requirements

All cases of second primary cancers, including acute myeloid leukemia (AML) and myelodysplastic syndrome (MDS), that occur following treatment on NCI-sponsored trials must be reported to ECOG-ACRIN using Medidata Rave

- **A second malignancy is a cancer that is UNRELATED to any prior anti-cancer treatment (including the treatment on this protocol). Second malignancies require ONLY routine reporting as follows:**
 1. Complete a Second Primary Form in Medidata Rave within 14 days.
 2. Upload a copy of the pathology report to ECOG-ACRIN via Medidata Rave confirming the diagnosis.
 3. If the patient has been diagnosed with AML/MDS, upload a copy of the cytogenetics report (if available) to ECOG-ACRIN via Medidata Rave.
- **A secondary malignancy is a cancer CAUSED BY any prior anti-cancer treatment (including the treatment on this protocol). Secondary malignancies require both routine and expedited reporting as follows:**
 1. Complete a Second Primary Form in Medidata Rave within 14 days
 2. Report the diagnosis via CTEP-AERS at <http://ctep.cancer.gov>
Report under a.) leukemia secondary to oncology chemotherapy, b.) myelodysplastic syndrome, or c.) treatment related secondary malignancy
 3. Upload a copy of the pathology report to ECOG-ACRIN via Medidata Rave and submit a copy to NCI/CTEP confirming the diagnosis.
 4. If the patient has been diagnosed with AML/MDS, upload a copy of the cytogenetics report (if available) to ECOG-ACRIN via Medidata Rave and submit a copy to NCI/CTEP.

NOTE: The Second Primary Form and the CTEP-AERS report should not be used to report recurrence or development of metastatic disease.

NOTE: If a patient has been enrolled in more than one NCI-sponsored study, the Second Primary Form must be

submitted for the most recent trial. ECOG-ACRIN must be provided with a copy of the form and the associated pathology report and cytogenetics report (if available) even if ECOG-ACRIN was not the patient's most recent trial.

NOTE: Once data regarding survival and remission status are no longer required by the protocol, no follow-up data should be submitted via CTEP-AERS or by the Second Primary Form.

Rev. Add22

3.4 Comprehensive Adverse Events and Potential Risks List (CAEPR) for Copanlisib dihydrochloride (BAY 80-6946 dihydrochloride, NSC 784727)

The Comprehensive Adverse Events and Potential Risks list (CAEPR) provides a single list of reported and/or potential adverse events (AE) associated with an agent using a uniform presentation of events by body system. In addition to the comprehensive list, a subset, the Specific Protocol Exceptions to Expedited Reporting (SPEER), appears in a separate column and is identified with bold and italicized text. This subset of AEs (SPEER) is a list of events that are protocol specific exceptions to expedited reporting to NCI (except as noted below). Refer to the 'CTEP, NCI Guidelines: Adverse Event Reporting Requirements' http://ctep.cancer.gov/protocolDevelopment/electronic_applications/docs/aeguidelines.pdf for further clarification. *Frequency is provided based on 702 patients.* Below is the CAEPR for Copanlisib dihydrochloride (BAY 80-6946 dihydrochloride).

NOTE: If an AE meets the reporting requirements of the protocol, and it is listed on the SPEER, it should ONLY be reported via CTEP-AERS if the grade being reported exceeds the grade listed in the parentheses next to the event in the SPEER.

Version 2.2, June 18, 2019¹

Adverse Events with Possible Relationship to Copanlisib dihydrochloride (BAY 80-6946 dihydrochloride) (CTCAE 5.0 Term) [n= 702]			Specific Protocol Exceptions to Expedited Reporting (SPEER)
Likely (>20%)	Less Likely (<=20%)	Rare but Serious (<3%)	
BLOOD AND LYMPHATIC SYSTEM DISORDERS			
	Anemia		Anemia (Gr 2)
		Febrile neutropenia	
GASTROINTESTINAL DISORDERS			
Diarrhea			Diarrhea (Gr 2)
	Mucositis oral		
Nausea			Nausea (Gr 2)
		Pancreatitis	
	Vomiting		Vomiting (Gr 2)
GENERAL DISORDERS AND ADMINISTRATION SITE CONDITIONS			
Fatigue			Fatigue (Gr 2)
INFECTIONS AND INFESTATIONS			
Infection ²			Infection² (Gr 2)
INVESTIGATIONS			
Neutrophil count decreased			Neutrophil count decreased (Gr 2)
	Platelet count decreased		Platelet count decreased (Gr 2)
	White blood cell decreased		
METABOLISM AND NUTRITION DISORDERS			
	Anorexia		Anorexia (Gr 2)
Hyperglycemia			Hyperglycemia (Gr 2)
MUSCULOSKELETAL AND CONNECTIVE TISSUE DISORDERS			
	Muscle cramp		Muscle cramp (Gr 2)
RESPIRATORY, THORACIC AND MEDIASTINAL DISORDERS			
	Pneumonitis ³		

Adverse Events with Possible Relationship to Copanlisib dihydrochloride (BAY 80-6946 dihydrochloride) (CTCAE 5.0 Term) [n= 702]			Specific Protocol Exceptions to Expedited Reporting (SPEER)
Likely (>20%)	Less Likely (<=20%)	Rare but Serious (<3%)	
SKIN AND SUBCUTANEOUS TISSUE DISORDERS			
		Erythroderma	
		Pruritus	
	Rash maculo-papular		Rash maculo-papular (Gr 2)
VASCULAR DISORDERS			
Hypertension			Hypertension (Gr 2)

¹This table will be updated as the toxicity profile of the agent is revised. Updates will be distributed to all Principal Investigators at the time of revision. The current version can be obtained by contacting [contact]. Your name, the name of the investigator, the protocol and the agent should be included in the e-mail.

²Infection includes all 75 sites of infection under the INFECTIONS AND INFESTATIONS SOC.

³Pneumonitis is a group term that includes interstitial lung disease, dyspnea, dyspnea at rest, and dyspnea exertional.

Adverse events reported on Copanlisib dihydrochloride (BAY 80-6946 dihydrochloride) trials, but for which there is insufficient evidence to suggest that there was a reasonable possibility that Copanlisib dihydrochloride (BAY 80-6946 dihydrochloride) caused the adverse event:

BLOOD AND LYMPHATIC SYSTEM DISORDERS - Eosinophilia

CARDIAC DISORDERS - Atrial fibrillation; Cardiac arrest; Left ventricular systolic dysfunction; Myocardial infarction; Sinus tachycardia

GASTROINTESTINAL DISORDERS - Abdominal pain; Colitis; Constipation; Dry mouth; Dyspepsia; Esophagitis; Flatulence; Gastritis; Gastroesophageal reflux disease; Oral dysesthesia; Oral pain; Upper gastrointestinal hemorrhage

GENERAL DISORDERS AND ADMINISTRATION SITE CONDITIONS - Chills; Death NOS; Fever; General disorders and administration site conditions - Other (failure to thrive); Non-cardiac chest pain

IMMUNE SYSTEM DISORDERS - Allergic reaction; Autoimmune disorder

INJURY, POISONING AND PROCEDURAL COMPLICATIONS - Fracture; Infusion related reaction; Injury, poisoning and procedural complications - Other (drug eruption)

INVESTIGATIONS - Activated partial thromboplastin time prolonged; Alanine aminotransferase increased; Alkaline phosphatase increased; Aspartate aminotransferase increased; Blood bilirubin increased; CPK increased; Ejection fraction decreased; Electrocardiogram QT corrected interval prolonged; Electrocardiogram T wave abnormal; Investigations - Other (electrocardiogram U wave abnormal); Lipase increased; Lymphocyte count decreased; Serum amylase increased

METABOLISM AND NUTRITION DISORDERS - Dehydration; Hypertriglyceridemia; Hyperuricemia; Hypocalcemia; Hypokalemia; Hypomagnesemia; Hyponatremia; Hypophosphatemia; Metabolism and nutrition disorders - Other (blood insulin increased)

MUSCULOSKELETAL AND CONNECTIVE TISSUE DISORDERS - Arthralgia; Generalized muscle weakness; Musculoskeletal and connective tissue disorder - Other (psoriatic arthropathy); Myalgia

NEOPLASMS BENIGN, MALIGNANT AND UNSPECIFIED (INCL CYSTS AND POLYPS) -
Tumor hemorrhage

NERVOUS SYSTEM DISORDERS - Amnesia; Dizziness; Dysesthesia; Dysgeusia; Headache; Paresthesia; Peripheral sensory neuropathy; Presyncope; Reversible posterior leukoencephalopathy syndrome

PSYCHIATRIC DISORDERS - Confusion

RENAL AND URINARY DISORDERS - Acute kidney injury; Renal and urinary disorders - Other (renal insufficiency)

RESPIRATORY, THORACIC AND MEDIASTINAL DISORDERS - Cough; Dyspnea³; Hypoxia; Pleural effusion; Pulmonary hypertension; Respiratory failure; Respiratory, thoracic and mediastinal disorders - Other (pulmonary congestion)

SKIN AND SUBCUTANEOUS TISSUE DISORDERS - Alopecia; Dry skin; Purpura; Rash acneiform; Stevens-Johnson syndrome

VASCULAR DISORDERS - Hypotension; Thromboembolic event; Vascular disorders - Other (circulatory collapse)

NOTE: Copanlisib dihydrochloride (BAY 80-6946 dihydrochloride) in combination with other agents could cause an exacerbation of any adverse event currently known to be caused by the other agent, or the combination may result in events never previously associated with either agent.

Rev. Add16

3.5 Dose Modifications

All toxicity grades below are described using the NCI Common Terminology Criteria for Adverse Events (CTCAE) version 5.0.

All appropriate treatment areas should have access to a copy of the CTCAE version 5.0. A copy of the CTCAE version 5.0 can be downloaded from the CTEP website

(http://ctep.cancer.gov/protocolDevelopment/electronic_applications/ctc.htm).

The side effects observed with copanlisib (BAY 80-6946) are consistent with those observed with other PI3K inhibitors.

Copanlisib will be administered at fixed dose (60 mg) intravenously on Days 1, 8, and 15 on a 28-Day cycle. Copanlisib dose reduction instructions provided in **Table 1** serve as guidelines to allow ongoing treatment for patients without signs or symptoms of progression while monitoring patient safety. If there is need to interrupt dosing for grade 3/4 toxicity, then there will be a dose reduction as per the table below, once toxicity improves to grade 1 or baseline. Selected toxicities / adverse events of interest for copanlisib include hyperglycemia, rash, hypertension, diarrhea.

Table 1 Overall Dose Modification Guideline for Copanlisib (BAY 80-6946)-Related Adverse Events

	Copanlisib
Starting dose	60 mg
First reduction	45 mg
Second reduction	30 mg

Dose may be suspended for up to 4 weeks due to toxicity. Patients requiring treatment to be held for >4 weeks will be taken off treatment. If treatment held for laboratory abnormality, recheck labs in one week. No dose reduction is allowed for patients treated at a dose 30 mg of copanlisib – if there is an indication for further dose reduction, the patient must permanently discontinue copanlisib. Dose re-escalation is not allowed after a dose reduction.

Rev. Add16

Dose Modification rules for transient post-infusion hyperglycemia

Patients who develop post-infusion glucose increases of grade 2 after study drug administration may continue treatment. However, the next infusion must be delayed until the patient's pre-infusion glucose levels return to < 160 mg/dL (fasting) or < 200mg/dL (non-fasting). Guidelines for the management of transient glucose increases are given in [Appendix III](#). Continuing occurrence of post-infusion blood glucose increases of grade ≥ 3 , despite optimal glucose lowering therapy after 2 infusions of copanlisib, will require dose reduction by one dose level.

- Further dose reduction (**where appropriate per study design/population**) is allowed as long as discontinuation criteria was not met.
- Dose re-escalation is allowed when a patient has achieved controlled glucose levels per investigator's judgment.

- Occurrence of post-infusion non-life threatening hyperglycemia requiring interventions at the protocol defined lowest dose level despite optimal glucose lowering therapy (after at least one cycle of treatment) requires permanent discontinuation of the study drug.
- Occurrence of post infusion life-threatening copanlisib related hyperglycemia requires permanent discontinuation of the study drug.

Management of Hyperglycemia

Metformin is the first antihyperglycemic medication of choice because of the lower risk of hypoglycemia with this agent. Because metformin in some patients may also cause diarrhea and can be poorly tolerated, other antihyperglycemic medications such as sulfonylureas (e.g. glimepiride, glipizide) can be used. Extra caution should be used with other drugs such as sulfonylureas because of the increased risk for hypoglycemia with these agents. Consultation with an endocrinologist can be helpful in managing hyperglycemia.

Insulin should only be used for patients with persistent, symptomatic hyperglycemia. It should not be used to lower glucose level on the day of infusion due to the risk of hypoglycemia. On treatment days, it is best to hydrate the patient and not give insulin to reduce glucose levels to meet study treatment criteria.

Management guidelines for fasting patients with hyperglycemia are listed below in Table 2.

Table 2: Management of Hyperglycemia

Grade	Intervention	Dose Adjustment
1	Initiation of an oral anti-hyperglycemic agent (e.g., metformin) and additional glucose monitoring should be considered.	No change.
2	Initiation or increased dose of an oral anti-hyperglycemic agent (e.g., metformin) and additional glucose monitoring should be considered.	Dosing with copanlisib may either be held or continued per Investigator evaluation.
3, asymptomatic	Patient should be managed as per standard care, including implementation of additional glucose monitoring and initiation and/or increase of anti-hyperglycemic therapy (e.g., metformin).	Consideration should be given to suspend copanlisib dosing until the hyperglycemia resolves to Grade \leq 2. Dosing with copanlisib may resume at the same dose level or at one dose level lower as outlined in Table 1 and after discussion with the Study Principal Investigator.
3, symptomatic (e.g., blurred vision, frequent urination, excessive thirst) or grade 4	Patient should be managed as per standard care, including implementation of additional glucose monitoring and initiation and/or increase of anti-hyperglycemic therapy	Copanlisib dosing should be suspended until the hyperglycemia resolves to Grade \leq 2. The patient will be discontinued from the study if such therapy fails to control their hyperglycemia. Dosing with copanlisib may otherwise resume at one dose level lower as outlined in Table 1.

*Based on fasting glucose level

Management of Rash

Treatment related rash has been reported with copanlisib. While most were CTCAE v3.0 Grade 1 or Grade 2 in severity, few patients experienced Grade 3 rash. Rash is generally macular or maculo-papular with or without pruritus, with some having developed desquamation. Patients with severe rash should be monitored for associated signs and symptoms, such as fever and hypotension that may be suggestive of a systemic hypersensitivity reaction. For severe rash, hold all study treatment until Grade ≤ 1 (see Table 3 below), and patients should be treated with supportive therapy per standard of care. Use of topical antihistamine, as well as topical or systemic corticosteroids, may be considered. There is no evidence for a phototoxic potential of copanlisib.

Table 3: Dose Delay and Modification Guidelines for Rash

Grade	Intervention	Dose Adjustment
Grade 1	Consider prescribing topical corticosteroids ^a	Continue dosing at current dose and monitor for change in severity.
Grade 2	Consider treatment with supportive therapy (e.g., topical or oral corticosteroids ^{a, b}).	Consider holding copanlisib or reducing to the next lower dose if rash is troublesome.
Grade 3 or 4	Consider treatment with supportive therapy (e.g., topical or oral corticosteroids ^{a, b}). Consider dermatological consultation. Consider obtaining photographs of rash if permitted by local regulations.	Hold all study treatment until Grade ≤ 1 . For Grade 3, restart copanlisib at the next lower dose upon discussion with Overall Principal Investigator, or permanently discontinue treatment. For Grade 4, permanently discontinue treatment

- a Suggested topical steroids include, hydrocortisone 2.5% to face twice daily, triamcinolone 0.1% or fluocinonide 0.1% cream to body bid.
- b Suggested oral steroids include methylprednisolone dose pack or prednisone 60 mg daily followed by a taper (e.g., 60 mg \times 2 days, 40 mg \times 2 days, 20 mg \times 2 days, etc.).

Management of Hypertension

Patients receiving copanlisib who have experienced hypertension and blood pressure should be monitored at each visit. In subjects with an initial BP reading within the hypertensive range, a second reading should be taken at least 2 minutes later, with the two readings averaged to obtain a final BP measurement.

For patients who develop HTN or worsening HTN during study treatment, antihypertensive medication should be initiated or optimized to achieve target blood pressure before interruption or dose reduction of the study treatment at the discretion of the investigator. If hypertension is persistent despite adequate anti-HTN therapy including titration of anti-HTN medication or introduction of additional anti-HTN medications, dose interruption, reduction or discontinuation is recommended. If Grade 4 HTN develops, permanently discontinue treatment. Patients with prior history of hypertension (on anti-hypertensive agents) should monitor/record their BP at home while on copanlisib.

It is important that patients with pre-existing arterial hypertension adhere to their regular medication schedule and take their usual doses on the days of study drug infusion.

The management of acute blood pressure (BP) increases following copanlisib will need to be individualized for each patient, but experience from a Bayer-sponsored phase 1 study with copanlisib has suggested the benefit of dihydropyridine calcium channel blockers (*i.e.*, amlodipine, felodipine). Nitrates should also be considered. Verapamil and diltiazem (non-dihydropyridine calcium channel blockers and moderate inhibitors of CYP3A4) should be used with caution due to a potential CYP3A4 interaction. In general, it is advisable for sites to be prepared, so that anti-hypertensive medication is readily available in case of need.

In the event of the occurrence of arterial hypertension $\geq 150/90$ mmHg during infusion of copanlisib at any cycle, antihypertensive treatment is suggested as indicated in [Appendix IV](#). In the event of the occurrence of grade 3 arterial hypertension ($\geq 160/100$ mmHg) during infusion of copanlisib, the infusion should be interrupted and anti-hypertensive treatment as suggested above is administered. Infusion can be resumed when BP has returned to $< 150/90$ mmHg.

Rev. Add16

Blood pressure measurement on treatment days

Blood pressure will be measured prior to each copanlisib dose (no more than 4 measurements) until there are two consecutive results $< 150/90$ mmHg with at least a 15 min interval between the measurements to be able to start the infusion of the study medication (pre-dose). The investigator can consider a medical intervention to maintain blood pressure in values appropriate for infusion. The investigator must delay the infusion until blood pressure values are below 150/90.

On copanlisib infusion days, blood pressure will be measured at pre dose, 30 min after the start of infusion, right after the end of infusion; and 1 h and 2 h after the end of copanlisib infusion.

NOTE: Time window of ± 10 min is allowed for all post dose blood pressure measurements.

Event	Management Guideline	Dose Modification	
Definitions used in the table:			
	
 - Persistent hypertension: Hypertension detected in two separate readings during up to three subsequent visits. - Well-controlled hypertension: Blood pressure of SBP \leq150 mmHg and DBP \leq90 mmHg in two separate readings during up to three subsequent visits. - Symptomatic hypertension: Hypertension associated with symptoms (e.g., headache, light-headedness, vertigo, tinnitus, episodes of fainting) that resolve after the blood pressure is controlled within the normal range. - Asymptomatic hypertension: SBP $>$150 mmHg and/or DBP $>$90 mmHg in the absence of the above symptoms. 		
(Scenario A)	
 • Asymptomatic and persistent SBP of \geq150 and $<$160 mmHg, or DBP \geq90 and $<$100 mmHg, OR • Clinically significant increase in DBP of 20 mmHg (but still below 100 mmHg). 	
 • Adjust current or initiate new antihypertensive medication(s). • Titrate antihypertensive medication(s) during the next 2 weeks to achieve well-controlled BP. If BP is not well-controlled within 2 weeks, consider referral to a specialist and go to scenario (B). 	
 • Continue copanlisib at the current dose.
(Scenario B)	
 • Asymptomatic SBP \geq 160 mmHg, or DBP \geq 100mmHg, OR • Failure to achieve well-controlled BP within 2 weeks in Scenario A. 	
 • Adjust current or initiate new antihypertensive medication(s). • Titrate antihypertensive medication(s) during the next 2 weeks to achieve well-controlled BP. 	
 • Interrupt copanlisib. • Once BP is well-controlled, restart copanlisib at a reduced dose.
(Scenario C)	
 • Symptomatic hypertension OR • Persistent SBP \geq160 mmHg, or DBP \geq100 mmHg, despite antihypertensive medication and dose reduction of study treatment 	
 • Adjust current or initiate new antihypertensive medication(s). • Titrate antihypertensive medication(s) during the next 2 weeks to achieve well-controlled BP. • Referral to a specialist for further evaluation and follow-up is recommended. • Continue follow-up per protocol. 	
 • Discontinue copanlisib.
(Scenario D)	
 • Refractory hypertension unresponsive to above interventions or hypertensive crisis. 	
 • Continue follow-up per protocol. 	
 • Discontinue copanlisib.

Non-infectious pneumonitis

The investigator is requested to differentiate between non-infectious pneumonitis, and infectious pneumonitis (viral, bacterial, or fungal), aspiration pneumonitis, or other pneumonitis clearly not due to a potential hypersensitivity reaction to the copanlisib infusion; and provide the basis for his/her assessment that it is infectious or other, as appropriate. The investigator is requested to report with the most specific clinical terms to describe the condition, not simple “pneumonitis”.

In the event of suspected non-infectious pneumonitis, modify copanlisib treatment as per table below.

Dose adjustment for non-infectious pneumonitis

Suspected or confirmed NIP per CTCAE	Action Taken	Re-treatment dose after recovery
Grade 1	No Change	NA
Grade 2	Dose Interruption Until recovery to ≤grade 1	Decrease dose to the next lowest dose level ^a
Grade 2 second re-occurrence	Permanent Discontinuation	NA
Grade 3	Permanent Discontinuation	NA
Grade 4	Permanent Discontinuation	NA

NA = Not applicable; NIP = Non-infectious pneumonitis; CTCAE = Common Terminology Criteria for Adverse Events.

a: Not applicable for 45 mg dose level. No re-escalation is allowed after the dose reduction.

Rev. Add16

The lowest dose level for patients with non-infectious pneumonitis is 45 mg; if a patient is already on the 45 mg dose level and cannot tolerate treatment study treatment will be discontinued permanently.

Rev. Add16

Dose modifications for Hematological Toxicities

Day	ANC		Platelets	Dose modifications
Day 1	≥ 500/uL	AND	≥ 75,000/uL	Treat at current dose level
	< 500/uL	OR	< 75,000/uL	Delay until count recovery

Use of WBC growth factors is allowed as per institutional guidelines for treatment or prevention of complication. Use of WBC growth factors to maintain dose intensity is not allowed.

Dose Modifications for General Non-hematologic Toxicities

This section does not refer to those non-hematologic toxicities for which dose modifications are listed above.

Grade	Action and Dose Modification
Grade 1 or transient Grade 2	No intervention
Grade 2 lasting \geq 7 days with optimal/best supportive care	Hold Copanlisib Resume at 60 mg after recovery to \leq grade 1 Recurrence at 60 mg: Hold Copanlisib Resume at 45 mg after recovery to \leq grade 1 Recurrence at 45 mg: Hold Copanlisib Resume at 30 mg after recovery to \leq grade 1 Recurrence at 30 mg: Discontinue Copanlisib
Grade 3	Hold Copanlisib Resume at 45 mg after recovery to \leq grade 1 Recurrence at 45 mg: Hold Copanlisib Resume at 30 mg after recovery to \leq grade 1 Recurrence at 30 mg: Discontinue Copanlisib
Grade 4	Discontinue treatment

Copanlisib will be discontinued if treatment delay is > 4 weeks

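### Section 3.5 both bans and permits dose re-escalation, and the first-event restart doses in the general non-hematologic table are right only for a patient still at 60 mg

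*Protocol*

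**What the plan says.** All of the following stands in Protocol Section 3.5.

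- **Overall rules, text around Table 1.** The dose levels are 60, 45 and 30 mg. "If there is need to interrupt dosing for grade 3/4 toxicity, then there will be a dose reduction as per the table below". At 30 mg, "if there is an indication for further dose reduction, the patient must permanently discontinue copanlisib". Finally, "Dose re-escalation is not allowed after a dose reduction".
- **Transient post-infusion hyperglycemia.** Repeated grade 3 or higher glucose rises lead to a reduction by one level. A bullet then says "Dose re-escalation is allowed when a patient has achieved controlled glucose levels", as judged by the investigator.
- **Rash, Table 3.** After grade 3 the instruction is relative to the current dose: "restart copanlisib at the next lower dose".
- **Non-infectious pneumonitis.** A footnote to its table repeats the ban: "No re-escalation is allowed after the dose reduction". The text below the table sets a separate floor: "The lowest dose level for patients with non-infectious pneumonitis is 45 mg".
- **General non-hematologic toxicities.** This table covers toxicities that have no rules of their own. For a first grade 2 event lasting at least 7 days it says "Hold Copanlisib Resume at 60 mg after recovery to" grade 1 or better. For a first grade 3 event it gives 45 mg in the same way. The lower steps in both rows apply to a recurrence at a named dose.

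**The concern.** There are two separate conflicts.

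1. The ban under Table 1 has no exception clause, and the hyperglycemia bullet does not present itself as one. A site that reduced a patient for glucose and later achieved control can cite the protocol for raising the dose and for not raising it.
2. The general non-hematologic table assumes that a patient having a first event is still on the starting dose. That need not be so. Hyperglycemia, rash, hypertension and pneumonitis each have their own reduction rules, so a patient can reach the general table at 45 or 30 mg. The listed restart dose is then higher than, or equal to, the dose at which the new toxicity occurred.

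The sequence is an ordinary one. The adverse event list in Section 3.4 puts hyperglycemia and hypertension among the likely events (above 20%). It does the same for diarrhea, nausea and fatigue, which have no dose table of their own and so fall under the general one. A patient reduced to 45 mg for glucose who then has prolonged grade 2 diarrhea would be restarted at 60 mg under the general table, which the overall rule forbids.

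**Working it through.** **Inputs.** Dose levels of 60, 45 and 30 mg (Table 1). First-event restarts of 60 mg for prolonged grade 2 and 45 mg for grade 3 (general non-hematologic table). Three overall rules: no re-escalation, a reduction after a grade 3/4 interruption, and discontinuation if a further reduction is indicated at 30 mg.

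**Calculation.** Relative change = restart dose ÷ current dose − 1, for each event type at each current dose, compared with what the overall rules allow.

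| First event | Current dose | Table restart | Ratio | Change | Overall rules | Agrees? |
|---|---|---|---|---|---|---|
| Grade 2, ≥7 days | 60 mg | 60 mg | 60/60 = 1.00 | 0% | at most 60 mg | yes |
| Grade 2, ≥7 days | 45 mg | 60 mg | 60/45 = 1.33 | +33% | at most 45 mg | no |
| Grade 2, ≥7 days | 30 mg | 60 mg | 60/30 = 2.00 | +100% | at most 30 mg | no |
| Grade 3 | 60 mg | 45 mg | 45/60 = 0.75 | −25% | 45 mg | yes |
| Grade 3 | 45 mg | 45 mg | 45/45 = 1.00 | 0% | 30 mg (30/45 = 0.67, −33%) | no |
| Grade 3 | 30 mg | 45 mg | 45/30 = 1.50 | +50% | discontinue | no |

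Two of the three grade 2 cells and two of the three grade 3 cells conflict: 2 + 2 = 4 of 6. Both agreeing cells are at 60 mg.

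**Qualifications.**
- The 30 mg cells need two earlier reductions. They cannot arise from pneumonitis alone, because of its 45 mg floor.
- For a patient at 45 mg after pneumonitis, the 60 mg restart also contradicts the pneumonitis footnote.
- The recurrence steps name the dose at which the recurrence happens, so they do not share this defect.

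**Can one precedence rule resolve both conflicts?**
- *The specific rule overrides the general.* The hyperglycemia bullet survives as an exception. The general non-hematologic table then also overrides the text around Table 1, and the four conflicting cells take effect.
- *The text around Table 1 prevails.* The four cells are corrected, but the hyperglycemia bullet has no effect.

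Neither choice leaves both provisions working.

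**The case against.** The strongest reply is that Section 3.5 is an overall guideline with exceptions by toxicity. The re-escalation bullet sits under its own hyperglycemia heading, is conditional, and appears deliberate. The section departs from its overall rules elsewhere: Table 2 lets asymptomatic grade 3 hyperglycemia resume at the same dose, and pneumonitis has its own floor. On this view the general non-hematologic table is simply silent about patients already reduced, and the explicit ban fills the gap. A site would have to disregard that ban to raise the dose. Section 3.5 itself calls the Table 1 instructions guidelines, and the MATCH Master Protocol, which is not shown, might settle precedence.

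Part of this stands. The hyperglycemia bullet may well be an intended exception, and many clinicians would not raise a dose after a new toxicity. But accepting that toxicity-specific text may depart from the overall rules is exactly what makes a literal reading of the general table defensible. That table is not silent either: it gives a number for a first event and does not limit it to patients at 60 mg.

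The scale is probably small. Section 1.2.6 reports that 5 of 57 patients (8.8%) in Study 12871 had an event leading to dose reduction. If that rate carried over to the accrual goal of 35, about 35 × 0.088 = 3 patients would have any reduction. The exact 95% interval for the rate, 2.9% to 19.3%, gives about 1 to 7. Only some of them would later meet the general table. The study pooled several dose levels, so this is indicative only.

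**Conclusion.** The concern holds. Within this document, re-escalation is both banned and permitted without a stated exception, and four of the six first-event restart cells contradict the overall rules: three raise the dose and one omits a required reduction. The percentages describe a literal reading of the table, not expected exposure in the trial. The conclusion rests on the text of this subprotocol alone; the master protocol was not available. How many patients would be affected cannot be derived, and neither the accrual goal nor any other stated statistical figure changes. It should still be fixed, because a dosing instruction followed as written can give the wrong dose after a new toxicity, and sites could reasonably treat the same event differently.

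**What to change.** 1. In the text under Table 1, either name post-infusion hyperglycemia as the sole exception to the re-escalation ban or delete the hyperglycemia bullet. The clinical team should decide which.
2. In the general non-hematologic table, replace the absolute first restarts with dose-relative ones, in the style that Table 3 already uses for rash. After a first grade 2 event lasting at least 7 days: resume at the current dose level. After grade 3: resume one level below the current dose, and discontinue if already at 30 mg.
3. Keep the 45 mg floor for patients with prior non-infectious pneumonitis, and say that it applies to this table too.

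The cost is a wording amendment to Section 3.5. Sample size, visits and procedures are unaffected.
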